**Figure 7-2. On-Treatment ALT/AST Monitoring Requiring Study Drug Withholding**

Subjects who develop signs or symptoms of liver toxicity (such as right upper quadrant discomfort, fever, nausea, vomiting, jaundice, rash, or eosinophilia > 5%) which are suspected by the principal investigator to be drug-related, must have study drug withheld and be placed into close observation.

If study drug is withheld, it may be reintroduced with approval from the Medical Monitor if another etiology of elevated liver tests is identified. Study drug must be discontinued if close monitoring is not possible or if total bilirubin, ALT or AST elevation recurs following re-challenge with study drug. Subjects who discontinue study drug due to suspected hepatotoxicity must be followed until symptoms subside, any abnormal laboratory values have resolved or returned to baseline levels, until there is a satisfactory explanation for the changes observed, or for 3 months after drug discontinuation, whichever is longer.

Treatment-emergent toxicities will be noted by the Investigator and brought to the attention of the Medical Monitor. Whether or not considered treatment-related, all subjects experiencing AEs must be monitored periodically until symptoms subside, any abnormal laboratory values have resolved or returned to baseline levels or they are considered irreversible, or until there is a satisfactory explanation for the changes observed.

Other than in the case of the liver enzymes noted above, Grade 3 or 4 clinically significant laboratory AEs should be confirmed by repeat testing as soon as practical to do so, and preferably within 3 calendar days of receipt of the original test results.

Any questions regarding toxicity management should be directed to the Medical Monitor.

## **7.6. Special Situations Reports**

### **7.6.1. Definitions of Special Situations**

Special situation reports include all reports of medication error, abuse, misuse, overdose, reports of adverse events associated with product complaints, occupational exposure with an AE, pregnancy reports regardless of an associated AE and AE in an infant following exposure from breastfeeding.

Medication error is any unintentional error in the prescribing, dispensing, or administration of a medicinal product while in the control of the health care provider, subject, or consumer.

Abuse is defined as persistent or sporadic intentional excessive use of a medicinal product by a subject.

Misuse is defined as any intentional and inappropriate use of a medicinal product that is not in accordance with the protocol instructions or the local prescribing information.

An overdose is defined as an accidental or intentional administration of a quantity of a medicinal product given per administration or cumulatively which is above the maximum recommended dose as per protocol or in the product labelling (as it applies to the daily dose of the subject in question). In cases of a discrepancy in drug accountability, overdose will be established only when it is clear that the subject has taken the excess dose(s). Overdose cannot be established when the subject cannot account for the discrepancy except in cases in which the investigator has reason to suspect that the subject has taken the additional dose(s).

Product complaint is defined as complaints arising from potential deviations in the manufacture, packaging, or distribution of the medicinal product.

Occupational exposure with an AE defined as exposure to a medicinal product as a result of one's professional or non-professional occupation.

### **7.6.2. Instructions for Reporting Special Situations**

#### **7.6.2.1. Instructions for Reporting Pregnancies**

The investigator should report pregnancies in female study subjects that are identified after initiation of study medication and throughout the study, including the post study drug follow-up period, to Gilead PVE using the paper pregnancy report form within 24 hours of becoming aware of the pregnancy. Reports should be sent directly to Gilead PVE at fax number **PPD** or email **PPD**

Refer to the eCRF completion guidelines for full instructions on the mechanism of pregnancy reporting.

The pregnancy itself is not considered an AE nor is an induced elective abortion to terminate a pregnancy without medical reasons.

Any premature termination of pregnancy (e.g., a spontaneous abortion, an induced therapeutic abortion due to complications or other medical reasons) must be reported within 24 hours as an SAE. The underlying medical reason for this procedure should be recorded as the AE term.

A spontaneous abortion is always considered to be an SAE and will be reported as described in Section 7.3. Furthermore, any SAE occurring as an adverse pregnancy outcome post study must be reported to Gilead PVE.

The subject should receive appropriate monitoring and care until the conclusion of the pregnancy. The outcome should be reported to Gilead PVE using the pregnancy outcome report form. If the end of the pregnancy occurs after the study has been completed, the outcome should be reported directly to Gilead PVE. Gilead PVE contact information is as follows:

Email: PPD and Fax: PPD

Pregnancies of female partners of male study subjects exposed to Gilead or other study drugs must also be reported and relevant information should be submitted to Gilead PVE using the pregnancy and pregnancy outcome forms within 24 hours. Monitoring of the female partner should continue until the conclusion of the pregnancy. If the end of the pregnancy occurs after the study has been completed, the outcome should be reported directly to Gilead PVE, fax number PPD or email PPD

Refer to [Appendix 3](#) for Pregnancy Precautions, Definition for Female of Childbearing Potential, and Contraceptive Requirements.

#### 7.6.2.2. Reporting Other Special Situations

All other special situation reports must be reported on the special situations report form and forwarded to Gilead PVE within 24 hours of the investigator becoming aware of the situation. These reports must consist of situations that involve study IMP and/or Gilead concomitant medications, but do not apply to non-Gilead concomitant medications.

Special situations involving non-Gilead concomitant medications do not need to be reported on the special situations report form; however, for special situations that result in AEs due to a non-Gilead concomitant medication, the AE should be reported on the AE form.

Any inappropriate use of concomitant medications prohibited by this protocol should not be reported as “misuse,” but may be more appropriately documented as a protocol deviation.

Refer to Section 7.3 and the eCRF completion guidelines for full instructions on the mechanism of special situations reporting.

All clinical sequelae in relation to these special situation reports will be reported as AEs or SAEs at the same time using the AE eCRF and/or the SAE report form. Details of the symptoms and signs, clinical management, and outcome will be reported, when available.

## **8. STATISTICAL CONSIDERATIONS**

### **8.1. Analysis Objectives and Endpoints**

Details will be provided in the statistical analysis plan (SAP).

#### **8.1.1. Analysis Objectives**

The primary objective of this study is as follows:

- To evaluate whether SEL can cause fibrosis regression and reduce progression to cirrhosis and associated complications in subjects with NASH and bridging (F3) fibrosis.

The secondary objective of this study is:

- To assess the safety and tolerability of SEL in subjects with NASH and bridging (F3) fibrosis.

The exploratory objectives of this study are as follows:

### **8.1.2. Primary Efficacy Endpoint**

The primary efficacy endpoint at Week 48 includes the proportion of subjects who achieve a  $\geq 1$ -stage improvement in fibrosis (according to the NASH CRN classification) without worsening of NASH (defined as a  $\geq 1$ -point increase in hepatocellular ballooning or lobular inflammation).

### **8.1.3. Clinical Efficacy Endpoint**

The clinical efficacy endpoint at Week 240 is EFS. EFS will be assessed by time to the first clinical event including progression to cirrhosis, liver decompensation events, liver transplantation, or all-cause mortality.

### **8.1.4. Secondary Endpoint**

The secondary endpoints of this study are as follows:

- Proportion of subjects who have progression to cirrhosis by Week 48;
- Proportion of subjects who have a  $\geq 1$ -stage improvement in fibrosis without worsening of NASH at Week 240;
- Proportion of subjects who have a  $\geq 1$ -stage improvement in fibrosis at Week 48 and Week 240;
- Proportion of subjects who have NASH resolution without worsening of fibrosis at Week 48 and Week 240.

### **8.1.5. Exploratory Endpoints**

**CCI**

## **8.2. Analysis Conventions**

All individual subject data will be listed as measured. All statistical summaries and analyses will be performed using Statistical Analysis System (SAS®) software (SAS Institute, Cary, North Carolina, USA).

### **8.2.1. Analysis Sets**

#### **8.2.1.1. Efficacy**

The primary analysis set for efficacy analyses will be the Full Analysis Set (FAS) which includes all subjects who were randomized into the study and received at least one dose of study drug.

Subjects who receive study drug other than that to which they were randomized will be analyzed according to the treatment group to which they were randomized.

#### 8.2.1.2. Safety

The primary analysis set for safety analyses will include all subjects who received at least one dose of study drug. Treatment-emergent data will be analyzed and defined as data collected from the first dose of study drug through the date of last dose of study drug plus 30 days. Subjects who received study drug other than that to which they were randomized will be analyzed according to the study drug received.

#### 8.2.1.3. Pharmacokinetics

The PK analysis set will include all randomized subjects who took at least one dose of study drugs and for whom concentration data of analytes SEL (and its metabolite GS-607509 as applicable) are available. The PK of other SEL metabolites may be explored.

CCI

#### 8.2.1.4. Biomarkers

The Biomarker Analysis Set will include data from subjects in the Safety Analysis Set who have the necessary baseline and on-study measurements to provide interpretable results for the specific parameters of interest.

### 8.3. Data Handling Conventions

Missing data can have an impact on the interpretation of the trial data. In general, values for missing data will not be imputed.

Where appropriate, safety data for subjects that did not complete the study will be included in summary statistics. For example, if a subject received study medication, the subject will be included in a summary of adverse events according to the treatment received; otherwise, if the subject is not dosed then they will be excluded from the summary. If safety laboratory results for a subject are missing for any reason at a time point, the subject will be excluded from the calculation of summary statistics for that time point. If the subject is missing a pre-dose value, then the subject will be excluded from the calculation of summary statistics for the pre-dose value and the change from pre-dose values.

Values for missing safety laboratory data will not be imputed; however, a missing baseline result will be replaced with a Screening result, if available. If no pre-treatment laboratory value is available, the baseline value will be assumed to be normal (i.e., no grade [Grade 0]) for the summary of graded laboratory abnormalities.

Values for missing vital signs data will not be imputed; however, a missing baseline result will be replaced with a Screening result, if available.

[figure not shown]
#### 8.4. Multiple Testing

When the primary histology efficacy endpoint is compared between each of the SEL arms and the placebo arm at Week 48, it will be tested at a two-sided 0.025 significance level to control an overall Type I error rate of 0.05 by Bonferroni adjustment.

The testing strategy for the clinical efficacy endpoint (EFS) is described below and is presented graphically in [Figure 8-1](#).

- 1) If the primary histology efficacy endpoint is significant in both SEL arms, the EFS endpoint will be tested for both SEL arms against placebo at Week 240 at a two-sided 0.05 significance level by the Hochberg procedure {[Hochberg 1988](#)}. If the larger p-value of SEL18 mg vs. placebo and SEL 6 mg vs. placebo is less than or equal to 0.05, the EFS endpoint for both SEL arms will be a success; if the larger p-value is  $> 0.05$ , the treatment arm with the larger p-value fails, and the smaller p-value will be compared with the significance level of 0.025 to determine the success of the treatment arm.
- 2) If the primary histology efficacy endpoint is significant in the SEL 18 mg but not the SEL 6 mg arm, the EFS endpoint will be tested for SEL 18 mg against placebo at Week 240 at a two-sided 0.025 significance level.
- 3) If the primary histology efficacy endpoint is significant in SEL 6 mg but not SEL18 mg arm, the EFS endpoint will be tested for SEL 6 mg against placebo at Week 240 at a two-sided 0.025 significance level.
- 4) If the primary histology efficacy endpoint is not significant in both the SEL 18 mg and SEL 6 mg arms, the trial will be terminated.

**Figure 8-1. Multiple Testing Flow Chart**

\* Nominal alpha will be adjusted using Haybittle-Peto approach

Although no formal statistical inference on EFS is planned at the Week 48 analysis, the actual nominal significance level for the EFS endpoint at the Week 240 analysis will be adjusted using the Haybittle-Peto approach {[Haybittle 1971](#)}. The adjustment will be based on the number of events at both the Week 48 and Week 240 analyses, assuming an allocation of a two-sided significance level of 0.001 at the Week 48 analysis.

## **8.5. Demographic Data and Baseline Characteristics**

Demographic and baseline measurements will be summarized using standard descriptive methods.

Demographic summaries will include sex, race/ethnicity, and age.

Baseline data will include a summary of body weight, height, BMI, and randomization stratification groups (presence or absence of diabetes; ELFTM score  $\geq 9.76$  or  $< 9.76$ ), and other disease characteristic variables.

Any discrepancies between the IWRS randomization stratification groups and the group assigned based on data entered in the database will be listed.

## **8.6. Efficacy Analysis**

### **8.6.1. Primary Efficacy Endpoints Analysis**

#### **Primary Histology Efficacy Endpoint Analysis**

A stratified MH test will be used to compare the differences in proportions of subjects who achieve a  $\geq 1$ -stage improvement in fibrosis without worsening of NASH at Week 48 between each of the SEL arms and the placebo arm, adjusting for stratification factors. Subjects with missing data regarding fibrosis stage and NAS elements used to define worsening of NASH (hepatocellular ballooning and lobular inflammation) at Week 48 will be analyzed as treatment failures. The point estimates and 95% confidence intervals for the differences in proportions will be calculated.

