After the multiple imputation, the pairwise logrank test will be performed to compare the survival rates between SEL 18 mg or SEL 6 mg and placebo on each complete data set (described in Section 6.2.3). Then, by combining the normalized chi-square statistics using Rubin's rule, the impact of departures from noninformative censoring can be investigated by

the combined treatment effect inference, which is a function of θ . Thus, the robustness of the significant results can be assessed.

The NRI approach will be used for the primary analysis of the primary histology efficacy endpoint and secondary endpoints evaluated at Week 48. LOCF analysis and OC analysis will be carried out as sensitivity analyses for these endpoints at Week 48 using the same analysis method as defined in Section 6.1.3. “Last observation” includes both baseline and postbaseline records, and only the records eligible for efficacy analysis will be carried forward.

The MI and TPA approaches will be used for the sensitivity analyses for the primary histology efficacy endpoint. KMMI approach will be used for the sensitivity analysis for the clinical efficacy endpoint.

The NRI approach will be used for the primary analysis for the secondary endpoints evaluated at Week 240. The LOCF and OC approaches will be used for sensitivity analysis of these endpoints.

CCI

In the subgroup analysis by body weight change from baseline, missing Week 48/Week 240 (for the Week 48/240 analysis, respectively) body weight will be imputed using the LOCF approach to determine which subgroup a subject belongs to.

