Baseline/OL-Baseline	1	(none)	1
Week 4/OL-Week 4	29	2	56
Week 12/OL-Week 12	85	57	126
Week 24/OL-Week 24	169	127	252
Week 48/OL-Week 48	337	253	420
Week 72/OL-Week 72	505	421	588
Week 96/OL-Week 96	673	589	756
Week 120/OL-Week 120	841	757	924
Week 144/OL-Week 144	1009	925	1092
Week 168/OL-Week 168	1177	1093	1260
Week 192/OL-Week 192	1345	1261	1428
Week 216/OL-Week 216	1513	1429	1596
Week 240/OL-Week 240	1681	1597	≥1681

Table 3-3. Analysis Visit Windows for ELF test score and components, FibroSure/FibroTest, α -Macroglobin, Haptoglobin, Apolipoprotein A1, C-Reactive Protein (CRP) and Total Bile Acids

Analysis Visit	Nominal Day	Lower Limit	Upper Limit
Baseline/OL-Baseline	1	(none)	1
Week 12/OL-Week 12	85	2	126
Week 24/OL-Week 24	169	127	252
Week 48/OL-Week 48	337	253	420
Week 72/OL-Week 72	505	421	588
Week 96/OL-Week 96	673	589	756
Week 120/OL-Week 120	841	757	924
Week 144/OL-Week 144	1009	925	1092
Week 168/OL-Week 168	1177	1093	1260
Week 192/OL-Week 192	1345	1261	1428
Week 216/OL-Week 216	1513	1429	1596
Week 240/OL-Week 240	1681	1597	≥1681

Table 3-4. Analysis Visit Windows for Elastography and Pooled Cohort Risk and Score

Analysis Visit	Nominal Day	Lower Limit	Upper Limit
Baseline	1	(none)	1 (28*)
Week 24	169	2(29*)	252
Week 48	337	253	420
Week 72	505	421	588
Week 96	673	589	840
Week 144	1009	841	1176
Week 192	1345	1177	1512
Week 240	1681	1513	≥1681

* for Elastography.

Table 3-5. Analysis Visit Windows for Cytokeratin-18 (CK-18) M30 and CK-18 M65

Analysis Visit	Nominal Day	Lower Limit	Upper Limit
Baseline	1	(none)	1
Week 24	169	2	252
Week 48	337	253	504
Week 96	673	505	840
Week 144	1009	841	1176
Week 192	1345	1177	1512
Week 240	1681	1513	≥1681

Table 3-6. Analysis Visit Windows for Biopsy Data

Analysis Visit	Nominal Day	Lower Limit	Upper Limit
Baseline	1	(none)	1
Week 48	337	169	504
Week 240	1681	505	≥1681

Data relating to unscheduled visits and early termination visits may be assigned to a particular visit or time point based on the visit windows. The following conventions will be followed:

- An unscheduled visit prior to the first dosing of study drug may be included in the calculation of the baseline value, if applicable.
- Unscheduled visits after the first dose of study drug will be included in determining the maximum postbaseline toxicity grade.
- Data collected on a follow-up visit will be summarized as a separate visit, and labeled “Follow-up Visit” for each phase.

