- For baseline, the last available record on or prior to the date of the first dose of study drug will be selected in the corresponding phase. If there are multiple records on the same day, the value with the lowest severity will be selected (eg, normal will be selected over abnormal for safety electrocardiogram [ECG] findings).
- For postbaseline visits, if there are multiple records on the same day, the value with the worst severity within the window will be selected (eg, abnormal will be selected over normal for safety ECG findings).

Postbaseline parameters used to define histology endpoints will be selected in each visit window according to the following rules:

- Histology endpoints including a ≥ 1 -stage improvement in fibrosis without worsening of NASH, progression to cirrhosis, ≥ 1 -stage improvement in fibrosis, NASH resolution without worsening of fibrosis, NAS and elements, SAF and elements will be derived based on parameters collected from 1 biopsy sampling date if the following 4 parameters are available: NASH CRN fibrosis stage, lobular inflammation, hepatocellular ballooning, and steatosis grades.
- When the set of the 4 parameters (NASH CRN fibrosis stage, lobular inflammation, hepatocellular ballooning, and steatosis grades) is available for multiple biopsy samples obtained on different dates in 1 visit window, the set with the biopsy sample collection date closest to the nominal day will be chosen for analysis.. When 2 samples are equidistant from the nominal day, the later set will be selected.
- When the set of the 4 parameters is not complete for any biopsy sample from a single day, the histology endpoints will be derived based on the nonmissing value of each individual parameter closest to the nominal day for that visit window. When 2 records are equidistant from the nominal day, the later record will be selected.
- For Ishak fibrosis stage, the nonmissing value from the biopsy sample collection date closest to the nominal day for the visit window will be selected regardless of the missing status of other parameters. When 2 records are equidistant from the nominal day, the later record will be selected.
- When an endpoint cannot be derived based on all biopsy samples in a visit window, the histology endpoint will be considered missing, and imputation methods listed in Section 3.6.1 will apply.

Liver stiffness by transient elastography data in each analysis visit window will be chosen based on the following rules:

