6.1. Primary Histology Efficacy Endpoint

6.1.1. Definition of Primary Histology Efficacy Endpoint

The primary histology efficacy endpoint at Week 48 is the proportion of subjects who achieve a ≥ 1 -stage improvement in fibrosis (according to the NASH CRN classification) without worsening of NASH (defined as a ≥ 1 point increase in hepatocellular ballooning or lobular inflammation).

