6.1.3. Analysis of Primary Histology Efficacy Endpoint

A stratified Mantel-Haenszel (MH) test will be used to compare the differences in proportions of subjects who achieve a ≥ 1 -stage improvement in fibrosis without worsening of NASH at Week 48 between SEL 18 mg (SEL 6 mg) and placebo, adjusting for the presence or absence of diabetes mellitus at baseline and ELF test score ≥ 9.76 or < 9.76 at baseline. Subjects with missing data regarding fibrosis stage and NAS elements used to define worsening of NASH (hepatocellular ballooning and lobular inflammation) at Week 48 will be analyzed as treatment failures for this endpoint. The 2-sided 95% CIs for the difference in proportions between SEL 18 mg (SEL 6 mg) and placebo will be constructed based on stratum-adjusted MH proportions as follows {Koch 1989}:

$$p_A - p_B \pm Z_{(1-\alpha/2)} * SE(p_A - p_B),$$

where

- $(p_A - p_B) = \frac{\sum w_h d_h}{\sum w_h}$, is the stratum-adjusted MH proportion difference, where $d_h = p_{Ah} - p_{Bh}$ is the difference in the proportion of subjects who achieved a ≥ 1 -stage improvement in fibrosis without worsening of NASH between SEL 18 mg (SEL 6 mg) and placebo in stratum h.

- $w_h = \frac{n_{Ah}n_{Bh}}{n_{Ah} + n_{Bh}}$, is the weight based on the harmonic mean of sample size per treatment group for each stratum where n_{Ah} and n_{Bh} are the sample sizes of SEL 18 mg (SEL 6 mg) and placebo in stratum h.

- $SE(p_A - p_B) = \sqrt{\frac{\sum w_h^2 \left[\frac{p_{Ah}^*(1-p_{Ah}^*)}{n_{Ah}-1} + \frac{p_{Bh}^*(1-p_{Bh}^*)}{n_{Bh}-1} \right]}{(\sum w_h)^2}}$, where

$$p_{Ah}^* = \frac{m_{Ah} + 0.5}{n_{Ah} + 1} \text{ and } p_{Bh}^* = \frac{m_{Bh} + 0.5}{n_{Bh} + 1}, \text{ and}$$

m_{Ah} and m_{Bh} are the number of subjects who achieved a ≥ 1 -stage improvement in fibrosis without worsening of NASH in SEL 18 mg (SEL 6 mg) and placebo in stratum h.

- $\alpha = 0.05$ for the calculation of 95% CI
- $Z_{(1-\alpha/2)} = Z_{0.975} = 1.96$ is the 97.5th percentile of the normal distribution
- $Z \text{ score} = \frac{(p_A - p_B)}{SE(p_A - p_B)}$

If the computed lower confidence bound is less than -1 , the lower bound is defined as -1 . If the computed upper confidence bound is greater than 1 , then the upper bound is defined as 1 .

The point estimates, 95% CIs, and corresponding p-values based on Z tests for the differences in proportions, and the 95% CIs for proportion of responders in each treatment group based on the Clopper-Pearson method will be calculated.

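### When a subject has two or more biopsies in the Week 48 window, SAP 3.8.3 can build the primary endpoint from different sampling dates and lets an unused steatosis grade decide which biopsy counts

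*Protocol*

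**What the plan says.** **Endpoint.** The Week 48 primary endpoint (Protocol 8.1.2, SAP 6.1.1) is at least one stage of fibrosis improvement without worsening of NASH. Worsening means at least a one-"point increase in hepatocellular ballooning or lobular inflammation". It needs three readings: NASH CRN stage, ballooning and lobular inflammation. Steatosis is not among them.

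**Missing data.** Protocol 8.6.1 says that subjects lacking the stage and the activity elements "used to define worsening of NASH (hepatocellular ballooning and lobular inflammation) at Week 48 will be analyzed as treatment failures". SAP 6.1.3 says that they "will be analyzed as treatment failures for this endpoint", and SAP 3.6.1 adds: "The NRI approach will be used for the primary analysis of the primary histology efficacy endpoint", where NRI is non-responder imputation.

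**Choosing the biopsy.** The window is in SAP 3.8.2, "Table 3-6. Analysis Visit Windows for Biopsy Data": Day 169 to Day 504, nominal Day 337. All biopsies before the first open-label day are eligible. SAP 3.8.3 then applies three steps:

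1. Histology endpoints come from one biopsy date "if the following 4 parameters are available: NASH CRN fibrosis stage, lobular inflammation, hepatocellular ballooning, and steatosis grades". If several biopsies are complete, "the set with the biopsy sample collection date closest to the nominal day will be chosen for analysis".
2. If no biopsy has all four, "the histology endpoints will be derived based on the nonmissing value of each individual parameter closest to the nominal day for that visit window".
3. Only if the endpoint still cannot be derived from all the biopsies in the window is it missing and sent to the imputation methods.

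**The concern.** Improvement without worsening is a joint finding about one tissue sample. Step 2 sets no same-date requirement, so the stage can come from one sample and the activity grades from another. The assembled value is then treated as observed. The failure rule does not reach it, and neither do the multiple imputation, tipping-point, LOCF and observed-case analyses, which act on missing endpoints or rely on the same derivation.

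Separately, a steatosis grade that plays no part in the primary endpoint decides whether a biopsy is complete, and so which biopsy is used.

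The endpoint carries weight. Under Protocol 8.4, a SEL arm goes on to EFS testing only if it succeeds here, and the trial is terminated if neither arm does. What makes a subject a responder should therefore be beyond argument.

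**Working it through.** **Is the design figure sound?** Inputs from Protocol 8.10: 320 and 160 subjects, 27% against 12%, two-sided alpha 0.025.
- Pooled rate = (160×0.12 + 320×0.27)/480 = 0.22; null SE = √[0.22×0.78×(1/160 + 1/320)] = 0.0401.
- Alternative SE = √(0.12×0.88/160 + 0.27×0.73/320) = 0.0357.
- Power = Φ[(0.15 − 2.241×0.0401)/0.0357] = 95.4%, against the stated 94%. With a continuity correction, 94% needs 161 placebo subjects against 160 planned. The stated figure is reproduced and is not in dispute.

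**How far apart can the parts be?** 504 − 169 = 335 days at the extreme. For Week 240 the window opens at Day 505 with no upper limit, so 1,681 − 505 = 1,176 days or more.

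**What does the rule do?** Protocol 4.2 requires F3 and at least grade 1 ballooning and inflammation at entry. In the cases below, F2 is therefore an improvement and grade 1 activity cannot be a worsening.

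| Case | Biopsies in the window | SAP 3.8.3 | One biopsy with all three readings |
|---|---|---|---|
| A | Day 300: F2 and steatosis only. Day 400: F3, inflammation 1, ballooning 1, no steatosis | F2 from Day 300 (37 days from nominal), activity from Day 400 (63 days): responder | Day 400, F3: non-responder |
| B | Day 337: F2, inflammation 1, ballooning 1, no steatosis. Day 200: all four, F3 | Day 200, F3: non-responder | Day 337, F2: responder |
| C | Day 169: inflammation 1, ballooning 1, steatosis. Day 504: F2 and steatosis | Assembled across 335 days: responder | None: missing, so failure |
| D | Day 337 only, lacking just steatosis, F2 | Day 337 used: responder | Same |
| E | Day 337 only, lacking ballooning | Missing, so failure | Same |

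Cases A and C create a responder that no single biopsy supports. In case A the Day 400 sample was sufficient by itself, and its stage is displaced only because steatosis was not graded. Case B goes the other way: an on-time responder is lost. Cases D and E show that with one biopsy the rule does no harm.

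**Size per subject**, at design rates with the SE held at 0.0357:
- Placebo: 1/160 = 0.63 points; 0.00625/0.0357 = 0.17 in Z.
- SEL: 1/320 = 0.31 points; 0.003125/0.0357 = 0.09 in Z.

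The documents give no frequency of multiple or incomplete biopsies, so no total can be computed.

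**The case against.** The strongest reply is that nothing here contradicts the Protocol, and that is right. A reader might infer that the SAP has abandoned the missing-equals-failure rule, or made a change that SAP 6.5 should have declared. The documents do not support that. SAP 6.1.3 and 3.6.1 keep the rule, the Protocol does not say how to choose among several biopsies, and Protocol 8.1 leaves details to the SAP. What remains is a derivation rule that narrows who counts as missing.

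Second, the circumstances are narrow. One-biopsy derivation is already the main rule, and only one biopsy is scheduled in this window. A second can arise as a repeat of an unacceptable sample (Protocol 6.11.13), on suspicion of cirrhosis (3.3.1) or at early termination (6.4.6). A repeat has no stated interval, so nothing suggests that gaps are typically long; 335 days is a limit. A reader might also infer that any biopsy without a steatosis grade is discarded; case D shows otherwise.

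Third, the rule is prespecified and does not depend on treatment. If equal shares of two arms became responders, the difference would not move (1/160 = 2/320), and cases A and B point in opposite directions. This stands: neither bias towards SEL nor Type I error inflation is shown.

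Fourth, a common four-parameter set keeps a subject's histology endpoints on one biopsy. That is a reasonable aim, but step 2 gives it up whenever no biopsy is complete, and case B shows its price.

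**Conclusion.** The point holds in a limited form. With two or more biopsies in Days 169 to 504, SAP 3.8.3 can score a responder whom no single biopsy supports. It can also set aside, in whole or part, a biopsy sufficient for the primary endpoint because of a reading that the endpoint does not use. The planned missing-data analyses would not reveal either.

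The effect is about 0.17 in Z per placebo subject and 0.09 per SEL subject, assuming 12% and 27%. It would matter only near the significance boundary. The number affected and the net direction are unknown. The width of the biopsy window is a different question: the Protocol's Week 48 visit window is minus 14 days (Table 6-1), and one complete biopsy far from Day 337 would still count after the change below.

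The case for acting is that the defect concerns the meaning of the gating endpoint and can be removed by wording alone.

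**What to change.** Amend SAP 3.8.3 as follows:

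- Derive the primary endpoint from one biopsy date that has NASH CRN stage, ballooning and lobular inflammation. If several qualify, use the one closest to Day 337, keeping the existing tie rule.
- Require steatosis only for NAS and SAF.
- Do not combine readings from different dates. If no single biopsy qualifies, the endpoint is missing and non-responder imputation applies.
- Apply the same one-biopsy rule to the other multi-parameter histology endpoints, including those at Week 240. NASH resolution without worsening of fibrosis uses the same three readings.

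**Cost.** No new data are needed. A few subjects who could have been assembled as responders become failures, and the primary endpoint and NAS or SAF may occasionally come from different biopsies. As an illustration only, assume that a share of subjects in every arm had an incomplete biopsy and all counted as failures. Pooled power would go from 95.4% to 94.8% at 2%, 93.9% at 5% and 92.1% at 10%. The true cost should be smaller, because only subjects with several biopsies whose readings could have been combined change status.
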